### **Accrual**

This trial will be an non-inferiority trial, intended to determine if a short course of methenamine hippurate is no worse than a short course of fluoroquinolones (ciprofloxacin at Pennsylvania Hospital, levofloxacin at HUP, based on current practice and fluoroquinolone availability at each site) in prevention of post-operative UTI in short-term indwelling catheterization. Our primary outcome is the treatment of UTI by symptoms, a clinically relevant outcome. In the only study to look at this primary outcome after treatment with prophylactic antibiotics during short-term catheterization in urogynecologic surgery, the percentage of patients requiring treatment for UTIs after prophylactic antibiotics was 22%. If we assume a non-inferiority margin of 15%, a clinically relevant margin and commonly used in non-inferiority/equivalence trials for studies examining antibiotic use for urinary tract infections, as well as 80% power and a one-sided alpha of 0.025, 120 participants in each arm (total of 240 patients) will be required. Of all patients that undergo pelvic reconstructive surgery at our institution, approximately 75% are discharged home with an indwelling catheter. With a potential 15% drop-out rate, we therefore anticipate that we will need to recruit about 370 eligible patients in our clinics. As listed before, review of the surgeons logs over the last 12 months shows that this study is feasible due to the large volume of pelvic reconstructive surgery procedures in Urogynecology and Urology. Last year, the combined surgical volume of these cases at our three clinics was 532 subjects; thus, we anticipate we will be able to easily recruit the proposed sample size in one year. We plan to

recruit women from 4 sites in 3 departments in the University of Pennsylvania Health System: 1) Urogynecology at Hospital of University of Pennsylvania (HUP), 2) Urogynecology at Pennsylvania Hospital (PAH) and 3) Urology at Pennsylvania Hospital (PAH). Physician investigators are present at all three sites, and will have opportunity to screen patients planning for surgery for pelvic organ prolapse, urinary incontinence, or both, for participation.

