**Procedures**

**RECRUITMENT** We plan to recruit women from 3 clinical sites associated with 3 departments in the University of Pennsylvania Health System: 1) Urogynecology at Hospital of University of Pennsylvania (HUP), 2) Urogynecology at Pennsylvania Hospital (PAH) and 3) Urology at Pennsylvania Hospital (PAH). Physician investigators, who are present at all sites, will screen patients planning for surgery for pelvic organ prolapse, urinary incontinence, or both, for participation. Following confirmation of eligibility, the physicians will obtain informed consent prior to surgery at the planned preoperative visit. Last year, the combined surgical volume of these cases at our three clinics was 532 subjects; thus, we anticipate we will be able to easily recruit the proposed sample size in twelve months. **ENROLLMENT AND BASELINE VISIT:** Patients who are being discharged home with an indwelling catheter following pelvic reconstructive surgery will be enrolled into the study. With regards to outpatient surgery (such as a suburethral sling), this will occur within a few hours after surgery for patients who fail their trial of void. Following inpatient surgery (such as sacrocolpopexy, uterosacral or sacrospinous ligament fixation, or colpocleisis), patients who are being discharged from the hospital with an indwelling catheter will be enrolled into the study. As per standard of care, all subjects will be scheduled for an office visit for catheter removal 24 to 72 hours after placement of the indwelling catheter per surgeon preference. Demographic information will be collected from the patients medical record (age, menopausal status, concurrent estrogen use, ethnicity, level of education, medical comorbidities, history of recurrent UTIs, and duration of hospitalization). Data regarding the patients surgical intervention (procedure type, surgical complications, operative time) will be collected from the operative record. At the time of catheter removal, subjects will be randomized to either methenamine hippurate or fluoroquinolones, using sealed, opaque, sequentially numbered envelopes. All patients, and all physicians and nurses directly involved in patient calls and clinical interaction, will be masked to treatment allocation. Only the nurses involved in catheter removal, but not decisions on the primary outcome, will open the envelope, and distribute the allocated medication to the patient, who will take one dose at the office. A 24-hour course of fluoroquinolones, as per AUA guidelines, are the first-line antibiotics for catheter removal, and will be one of the active arms of the study. Due to differences of office practice and formulary availability, the fluoroquinolone of choice at each site will be different; this is clinically relevant as different urology practices across the country use different fluoroquinolones for prophylaxis. At HUP and Radnor, the 24 hour course of fluoroquinolone used will be one dose of 500 mg of levofloxacin, as per office practice and formulary availability. At the other sites (Pennsylvania Hospital, Chestnut Hill Hospital), the 24 hour course of fluoroquinolone as per office practice will be two doses of 500 mg of ciprofloxacin, 12 hours apart. Methenamine hippurate will be given as two doses of 1g of methenamine hippurate, taken 12 hours apart. The patient will not be told which

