**Analysis Plan**

Categorical variables will be analyzed using chi-squared or Fishers exact test and parametric or non-parametric t-tests for continuous variables. Bivariable analysis will be used to determine variables (risk factors) that are independently associated with post-operative UTI. Duration of catheterization between groups will be compared using the Mann-Whitney test to compare difference in medians. The primary outcome will be the rate of clinically suspected UTI requiring treatment within the first three weeks following surgery. Comparison with fluoroquinolones will be performed using relative risk ratio. Analysis will be performed by intention to treat. If imbalances in baseline demographics are identified, multivariate analyses for post-operative UTI will be performed to control the inequality. Cost-effectiveness analysis will be performed by monetizing the collected resource utilization data in each treatment arm, including use of intervention resources, UTI treatment resources, as well as primary and secondary care resources. Incremental cost-effectiveness ratios will be calculated to compare difference in costs between prophylaxis with methenamine and prophylaxis with fluoroquinolones to the difference in effect on the incidence of post-operative UTI. Prevalence of adverse effects will be measured as

percentages. Rate of urine cultures performed by patients treated for symptomatic UTI, as well as the rate of culture-positive UTI will be noted; comparison with fluoroquinolones will be performed using relative risk ratio, with analysis by intention to treat. Positive cultures will be analyzed for percentage of uropathogen type, type of uropathogen showing resistance, and overall percentage of cultures showing resistance.

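### The sample size rests on a 15-point risk difference, but the Analysis Plan compares arms by relative risk with no margin, confidence limit or non-inferiority rule

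*Combined protocol and SAP*

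**What the plan says.** The Objectives and Accrual sections both state a non-inferiority aim. Accrual gives the design inputs: "If we assume a non-inferiority margin of 15" per cent, a 22% rate of treated UTI after prophylactic antibiotics, 80% power and one-sided alpha 0.025, leading to 120 per arm. It does not say whether the 15% is absolute or relative.

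The Analysis Plan names the three-week treated-UTI rate as the primary outcome and specifies intention to treat. Its only statement on how the primary outcome is compared is "Comparison with fluoroquinolones will be performed using relative risk ratio". Non-inferiority, the margin, alpha and a confidence limit do not appear in that section.

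On adjustment it says "If imbalances in baseline demographics are identified, multivariate analyses for post-operative UTI will be performed to control the inequality". The Procedures section lists what is collected as demographic information ("age, menopausal status, concurrent estrogen use, ethnicity, level of education, medical comorbidities, history of recurrent UTIs, and duration of hospitalization"). The Analysis Plan does not say which items could enter a model, what counts as an imbalance, what the model is, or whether its result can displace the crude one.

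The comparator is a pooled fluoroquinolone group, with the drug set by site: "ciprofloxacin at Pennsylvania Hospital, levofloxacin at HUP, based on current practice and fluoroquinolone availability at each site". Procedures gives a reason for accepting this: "this is clinically relevant as different urology practices across the country use different fluoroquinolones for prophylaxis".

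**The concern.** A non-inferiority conclusion depends on one upper confidence limit set against one margin on one scale. Here the margin belongs to the risk difference and the planned estimate is a ratio, so the analysis as written cannot produce the conclusion for which the trial was sized. An analyst would have to supply the missing step, by converting the margin to a ratio, by switching to a difference, or by reading a non-significant ratio as success. These routes can give different verdicts on the same data, and only the second has the stated 80% power. The third is the most damaging, because failing to find a difference is not evidence that it is smaller than 15 points. The open question of crude or adjusted adds a smaller ambiguity of the same kind.

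**Working it through.** **Inputs.** From Accrual: comparator risk 22%, margin 15%, one-sided alpha 0.025 (z = 1.960), power 80% (z = 0.842), 120 per arm. Assumed: the same 22% in the methenamine arm when there is no true difference.

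**1. Reproduce the plan's figure.** On the risk difference, with unpooled variance:

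n per arm = 2 × 0.22 × 0.78 × (1.960 + 0.842)² / 0.15² = 119.7, so 120.

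This matches the stated figure, and power at 120 per arm is 80.1%. A restricted-variance (Farrington-Manning) version gives 121.5. If 15% were instead relative to 22%, the margin would be 0.15 × 0.22 = 0.033 and the same formula would give 0.3432 × 7.849 / 0.033² ≈ 2,474 per arm. The margin behind 120 is therefore 15 absolute points.

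**2. Convert to the planned scale (illustration).** Fifteen points above 22% is 37/22 = 1.68 as a relative risk.

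- SE(ln RR) = √(2 × (0.78/0.22)/120) = 0.243
- Power = Φ(ln 1.68/0.243 − 1.96) = Φ(0.18) = 57%
- Needed for 80% power: 2 × (0.78/0.22) × (1.960 + 0.842)² / (ln 1.68)² = 206 per arm

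**3. How often the verdicts differ.** In 400,000 simulated trials with 120 per arm, 22% in both arms and an upper 97.5% limit, the difference passes in 80.3%, the ratio passes in 57.2%, and they disagree in 23.1%.

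A single example is 28/120 methenamine against 26/120 fluoroquinolone events.

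- Difference: 1.7 points, upper limit 1.7 + 1.96 × 5.39 = 12.2 points. This passes.
- Ratio: 1.077, upper limit exp(0.074 + 1.96 × 0.240) = 1.72. This fails against 1.68.

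**4. Non-significance as the criterion.** With true risks of 37% and 22%, exactly at the margin, 20,000 simulated trials gave a non-significant ratio in about 28%. The planned error there is 2.5%.

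**5. The equivalence depends on the control risk.** Fifteen points corresponds to a relative risk of 25/10 = 2.50 at 10%, 30/15 = 2.00 at 15%, 37/22 = 1.68 at 22% and 45/30 = 1.50 at 30%. No single ratio margin stands in for 15 points.

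**6. Cost of the fix in sample size.** None: the risk difference against 15 points is the calculation in step 1.

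**The case against.** The plan is less open than a quick reading suggests. It names a default estimate (a crude relative risk) and an analysis set, and the margin and alpha do exist, in Accrual. The natural reading is that the crude ratio is primary and adjustment supportive. This stands. The defect is that margin and analysis are not connected and sit on different scales, not that nothing is specified.

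The 57% and 23% figures rest on a ratio margin that the documents never give. This also stands, so they show how large the mismatch can be and are not a forecast of what the trial will do. If the ratio margin were re-derived at other control risks (2.0 at 15%, 1.5 at 30%), power on the ratio would be about 62% and 54%, against 90% and 72% on the difference. The gap remains.

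Two stronger readings are tempting, and the documents do not support either.

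- **Pooling two fluoroquinolones is an error, or the primary analysis must be stratified by drug.** Pooling is deliberate, a reason is given, and it does not bias the comparison. In simulation, stratifying changed power by −0.2 to +2.1 points, with the gain needing an assumed gap of up to 20 points between site groups. Methenamine patients receive no fluoroquinolone, so the stratum is really a group of sites, and any drug effect is confounded with site.
- **The imbalance clause seriously inflates type I error.** A figure of 3.6–4.3% arises only if the analyst picks freely among all 256 subsets of eight assumed covariates. The clause allows adjustment only for imbalances that are found. When the choice was restricted to covariates imbalanced at p < 0.05, 0.10 or 0.20, simulated error was 2.5–2.6%, 2.6–2.7% and 2.9–3.1%, against 2.3–2.4% unadjusted (Monte Carlo error about 0.2 points). A fixed 5% rule gave 2.5%. What is missing is a statement of which result decides.

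**Conclusion.** The point holds. The sample size is for a 15-point risk difference, while the analysis is a relative risk with no margin, limit or rule, so the plan as written delivers neither the stated non-inferiority conclusion nor its 80% power. The scale is the main defect. The silence on crude or adjusted is secondary, and the choice of fluoroquinolone is not a defect in the analysis.

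Size: about 57% against 80% power and about 23% discordant verdicts, if the margin is converted to 1.68. If non-significance were taken as success, about 28% of trials of a treatment 15 points worse would look acceptable. The plan does not say that it would use that criterion; nothing in it rules it out.

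These figures assume 22% in the fluoroquinolone arm and 120 per arm analysed. The Study duration section gives a different target, 72 per arm, at which power on the difference would be Φ(0.15/√(0.3432/72) − 1.96) = 58%. That conflict is a separate matter to reconcile.

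**What to change.** Replace the comparison sentence and the imbalance sentence in the Analysis Plan with a rule such as this:

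*The primary analysis is the unadjusted risk difference, methenamine minus pooled fluoroquinolone, by intention to treat. Non-inferiority is shown if the upper limit of the two-sided 95% confidence interval is below 15 percentage points. The relative risk with its 95% confidence interval is secondary. Any covariate-adjusted analysis is supportive and cannot replace the primary result.*

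In Accrual, state that the 15% is in absolute percentage points.

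Stratifying by the fluoroquinolone designated for the site is optional. If it is done, the list of sites and their drugs must first be made consistent across sections. Results by site drug should be descriptive only: power is 37%, 51% and 63% with 40, 60 and 80 per arm.

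The cost is wording alone, with no new data and no change to 120 per arm. The downside is that a fixed 15-point margin is more permissive in relative terms when the fluoroquinolone risk is below 22% (10% against 25% is a relative risk of 2.5), which is why the relative risk should be shown beside it. How the anticipated 15% drop-outs are counted would still need its own rule.

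The Study duration section schedules data collection for 2014–2015 and the document is dated 2019, so the data may already be unblinded. In that case, label the risk difference post hoc and report it together with the pre-specified relative risk.

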## **Protocol**

**Abstract**

Catheter-associated urinary tract infection (UTI) is the most common post-operative nosocomial infection. An agent that prevents catheter-associated UTI but is not associated with antibiotic resistance is not known. Methenamine hippurate has similar pharmacokinetics as short-course antibiotics that prevent catheter-associated UTI, such as ciprofloxacin. Our aim is to compare the efficacy of an innovative short regimen of methenamine hippurate, an antiseptic that is converted into formaldehyde in urine, with the efficacy of short-course ciprofloxacin for preventing post-operative UTI in urogynecologic surgery. We propose a randomized, blinded non-inferiority trial to determine the efficacy of two doses of methenamine hippurate compared with the urology standard of fluoroquinolones at catheter withdrawal for reducing post-operative UTI in patients requiring short-term indwelling catheterization after pelvic reconstructive surgery. The primary outcome will be the rate of symptomatic UTI requiring treatment within three weeks of surgery. We will perform cost-effectiveness analysis comparing the cost of prophylaxis with methenamine to the cost of prophylaxis with ciprofloxacin. We plan to describe the resistance profile of positive urine cultures and adverse effects of methenamine. This study is innovative because it involves 1) a two-dose regimen of a non-antibiotic prophylactic and 2) cost-effectiveness analysis. The findings will help reduce the rate of antibiotic use and nosocomial UTIs, which are associated with morbidity and serve as important indicators of quality of care.

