**Objectives**

**Overall objectives**

SPECIFIC AIMS Primary Aim: To determine if the efficacy of prophylaxis with a 24 hour course of methenamine hippurate (two doses) is non-inferior to the efficacy of a 24-hour course of fluoroquinolones in prevention of post-operative urinary tract infections after short-term indwelling catheterization following surgery for pelvic floor disorders. Secondary aim: - To determine if prophylaxis with methenamine hippurate is more cost-effective than prophylaxis with fluoroquinolones

in patients undergoing short-term indwelling catheterization. - To determine the antibiotic resistance profile of post-operative urinary tract infections that develop after short-term indwelling catheterization after surgery for pelvic floor disorders, with methenamine as compared to fluoroquinolones. - To determine the prevalence of side effects that may accompany use of methenamine hippurate prophylaxis. - To describe factors that influence patient medication compliance with short-term methenamine hippurate and ciprofloxacin prophylaxis.

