#### **Secondary outcome variable(s)**

SECONDARY OUTCOME: - cost-effectiveness of prophylaxis with methenamine hippurate for prevention of post-operative UTI compared to prophylaxis with fluoroquinolones - rate of culture-positive symptomatic UTI - prevalence of antibiotic resistance in positive post-operative cultures - prevalence of side effects following a 24-hour course of methenamine hippurate - factors that may influence patient compliance with short-course of chemoprophylaxis. Cost-effectiveness data: We plan to perform a cost-effectiveness analysis from a societal perspective, which will be expressed as incremental cost per UTI prevented. Routine costs of prevention of UTI with methenamine hippurate prophylaxis will be compared with costs of prevention of UTI with fluoroquinolone prophylaxis. We plan to capture incremental direct health care costs, which will be estimated using the resource costing method. Direct medical service standard of care use (such as number and types of physician visits, hospital admissions lengths, emergency transport and emergency room visits), and direct medical costs (such as antibiotic treatment of UTI, prophylaxis with methenamine or ciprofloxacin, urine laboratory tests, or treatment of complications like pyelonephritis) will be monetized by multiplying the number of units of each resource used per treatment arm by the average unit cost of these items in dollars. Detailed individual cost data will not be collected. This method allows a consistent capture of resource use when costs are incurred across multiple health systems or payers. Cost for each direct medical service use, direct non-medical items, and indirect items will be assigned based on national Medicare reimbursement rates or other standardized unit costs. Among patients who undergo urine culture as part of standard of care for UTI, the rate of positive cultures will be identified. As per standard of care, antibiotic resistance will be collected by sensitivity testing on all positive urine cultures identified from samples collected for evaluation of symptomatic UTI in post-operative patients. Bacterial species and sensitivities will be identified and recorded. To determine medication compliance rates, any unused medication will be returned to the office at their post-operative follow-up visit. As per routine care, investigators will also ask patients during the weekly routine post-operative call and routine post-operative visits about their compliance with the second dose of medication. Adverse effects from the administration of methenamine and fluoroquinolones will be collected. Patients will be asked to document any side effects, including nausea, vomiting, pruritis, and rash, that may occur within 24 hours of the administration of the last dose of methenamine or antibiotic.

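### The cost-effectiveness aim is summarised by a ratio built from arm totals, with no interval and no rule for a UTI difference that is zero, near zero or favours fluoroquinolones

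*Combined protocol and SAP*

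**What the plan says.** Cost-effectiveness is in the trial's title. It is also one of the secondary aims under Overall objectives: "To determine if prophylaxis with methenamine hippurate is more cost-effective than prophylaxis with fluoroquinolones".

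The section Secondary outcome variable(s) fixes the summary measure, "which will be expressed as incremental cost per UTI prevented", and the costing method: "multiplying the number of units of each resource used per treatment arm by the average unit cost of these items in dollars". It adds: "Detailed individual cost data will not be collected". The Analysis Plan then gives the calculation: "Incremental cost-effectiveness ratios will be calculated to compare difference in costs between prophylaxis with methenamine and prophylaxis with fluoroquinolones to the difference in effect" on UTI incidence.

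Two other statements bear on what a reader would see. Costs in the two arms are to be set against each other ("Routine costs of prevention of UTI with methenamine hippurate prophylaxis will be compared with costs of prevention of UTI with fluoroquinolone prophylaxis"; the Abstract says much the same). UTI itself is compared on the relative scale: "Comparison with fluoroquinolones will be performed using relative risk ratio".

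For this aim the document mentions no confidence interval, bootstrap, net benefit, willingness-to-pay value or sensitivity analysis. It does not say how to report one arm being both cheaper and better, or a UTI difference of zero or in the unexpected direction.

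**The concern.** A cost per infection avoided suits a trial that expects one arm to avoid infections. This is a non-inferiority trial, and its sample size is consistent with equal UTI rates. The denominator of the ratio is the absolute UTI difference, so under that planning case the method divides by a quantity centred on zero.

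Three problems follow.

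- **Instability.** When the observed difference is one or two events, the ratio can be very large, change sign or be undefined.
- **Ambiguous sign.** A negative ratio arises when methenamine is cheaper and better, and also when it is dearer and worse. A positive ratio may be a cost per UTI avoided, or money saved per extra UTI.
- **No error bar.** Totals by arm carry no between-patient variation in cost, so the general tests listed in the Analysis Plan cannot be applied to them. A relative risk, even with an interval, gives neither the interval for the absolute difference nor its joint variation with cost.

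At stake is whether a claim that methenamine is more cost-effective could rest on a point estimate driven by one or two chance events.

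**Working it through.** **Inputs.** From Accrual: 22% UTI treatment rate after antibiotic prophylaxis, margin 15 points, 80% power, one-sided alpha 0.025, 120 per arm. From Study duration: a conflicting 72 per arm. From Background, for illustration only: about $600 per UTI, methenamine about $2 per pill, commonly used antibiotic prophylaxis $3 to $17 per pill.

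**Step 1: reproduce the plan's figure.** With 22% in both arms,

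n = (1.95996 + 0.84162)² × 2 × 0.22 × 0.78 / 0.15² = 7.849 × 0.3432 / 0.0225 = 119.7, hence 120 per arm.

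The plan's figure reproduces. The 22% for methenamine is inferred from this agreement and is not stated.

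**Step 2: precision of the denominator.** SE = √(2 × 0.22 × 0.78 / n).

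- n = 120: √0.00286 = 0.0535, about 5.3 points; 95% half-width 1.96 × 0.0535 = 0.105, about 10.5 points.
- n = 72: 0.0690, or 6.9 points; half-width 13.5 points.

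**Step 3: how often the ratio is undefined or rests on very few events.** These are exact binomial probabilities over all pairs of event counts, with fluoroquinolones at 22%.

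| n per arm | Methenamine rate | Equal counts (ratio undefined) | Differ by two UTIs or fewer | More UTIs with methenamine |
|---|---|---|---|---|
| 120 | 22% | 6.2% | 30.3% | 46.9% |
| 120 | 17% | 4.0% | 20.1% | 14.4% |
| 120 | 27% | 4.0% | 19.9% | 79.6% |
| 72 | 22% | 8.0% | 38.6% | 46.0% |

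Hand check of the first row: the count difference has SD √(2 × 120 × 0.22 × 0.78) = 6.42. The chance of a tie is about 1/(6.42 × 2.507) = 0.062, and (1 − 0.062)/2 = 0.469.

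**Step 4: illustration of the sign problem.** Assumptions: one pill per dose, two doses in each arm, $600 per UTI, no other costs, 120 per arm. Let dE be UTIs avoided per patient with methenamine and g the drug-cost difference, so dC = g − 600 × dE. Then g = 4 − 6 = −$2 at a $3 antibiotic pill, and g = 4 − 34 = −$30 at $17.

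| UTIs: fluoroquinolone, methenamine | Antibiotic pill | dE | dC per patient | Ratio | Meaning for methenamine |
|---|---|---|---|---|---|
| 25, 27 | $3 | −2/120 | +$8 | −$480 | dearer and worse |
| 25, 27 | $17 | −2/120 | −$20 | +$1,200 | saves $1,200 per extra UTI |
| 27, 25 | $3 | +2/120 | −$12 | −$720 | cheaper and better |
| 27, 25 | $17 | +2/120 | −$40 | −$2,400 | cheaper and better |

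The ratios −$480 and −$720 look alike and mean opposite things. The 95% interval for dE is −12.1 to 8.8 points in the first pair and −8.8 to 12.1 in the second. The intervals for dC, in row order, are −$55 to $71, −$83 to $42, −$75 to $51 and −$103 to $23. They carry UTI variation only, so they are minimum widths. All include zero.

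**The case against.** The strongest reply is that the plan already produces the parts of the ratio. Costs by arm are compared and UTI rates by arm are compared, so the quadrant can be read off. A reader might infer from the sign ambiguity that the plan would hide which arm did better. The documents do not support that. What stands is that the uncertainty cannot be recovered from arm totals, and that nothing commits the report to naming the quadrant.

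A second reply is that the Analysis Plan states no interval for any comparison, so this is one instance of a wider gap. That is partly right. What is particular to this aim is the joint uncertainty of cost and effect, which an interval on the relative risk would not supply.

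Third, a reader might point out that, at equal true rates, the interval for the UTI difference includes zero in about 95% of trials, and treat this as proof that the ratio misleads. It is only nominal coverage. High figures at other true rates would reflect limited power for a secondary comparison that the trial was not sized for. The relevant figures are those for ties and very small differences.

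Fourth, the dollar model is thin. The Procedures section gives a single levofloxacin dose at some sites; at $3 with one pill, g becomes 4 − 3 = +$1 instead of −$2, so its sign flips. The $3 to $17 range is not specific to a fluoroquinolone, and a societal perspective takes in costs left out here. This objection stands in full. The examples show how the sign behaves and do not forecast the trial's result.

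**Conclusion.** The point holds as a cheap improvement. The stated method yields a point estimate with no error bar and no rule for the cases in which it breaks down. Under the rate that reproduces the sample size, those cases are common: undefined in 6.2% of trials, two UTIs or fewer between the arms in 30%, and more UTIs with methenamine in 47%. This rests on equal 22% rates, which is an inference. If methenamine's true rate is five points higher or lower, a gap of two UTIs or fewer still occurs in about 20%. With 72 per arm the equal-rate figures for ties and small gaps rise to 8.0% and 39%.

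A reader might infer that the primary non-inferiority comparison or its sample size is affected; neither is. A reader might also take the ratios in dollars as predictions. The documents do not fix unit prices, so they cannot be.

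**What to change.** In Secondary outcome variable(s) and the Analysis Plan:

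1. State that resource counts are kept by patient and that the standard unit costs are applied to those counts.
2. Report the cost difference and the absolute UTI difference separately, each with a 95% confidence interval. Use a patient-level bootstrap for cost, drawn jointly with UTI.
3. Report the ratio only with its quadrant, and as undefined when the UTI difference is zero. Do not claim that methenamine is more cost-effective from the point estimate alone.
4. Optional: a cost-effectiveness plane, or net benefit over a pre-stated range of values per UTI avoided.

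The cost is some wording and a little more analysis. The decision not to collect detailed individual costs is no obstacle, because standard prices are applied to individual counts. The structured calls in Procedures already ask each patient about UTI treatment, urine tests and visits, and Subject Confidentiality has data recorded under a subject number.

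It should not be assumed that no new data are needed. Admission length, emergency transport and indirect items are to be costed but are not named in the structured calls, so the team must confirm that they are recorded by patient. The result will often look inconclusive, and the change adds no power.
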